Despite the high success rate of anti-reflux surgery, reoperation does occur. The indication for reoperation is most often recurrence of reflux symptoms or dysphagia, and reoperation should be preceded by thorough investigation and possible endoscopic balloon-dilation (15). Laparoscopic reoperation is both feasible and safe, but has been linked to higher morbidity, higher risk of conversion to open surgery and longer length of stay. The final result seem to result in less patient satisfaction than primary surgery, but the available evidence is limited by a high risk of bias due to small sample size and a possible underreporting of complications (16, 17).

An American study reported a cumulative five- and ten year incidence of reoperation of 5.2% and 6.9% respectively. The rate of reoperation was highest in the first year after primary anti-reflux surgery. 30% of reoperations were performed in a different center than the primary procedure. In a Danish study, Funch-Jensen et al (18), investigated rate of reoperation in Denmark 1997-2005 and calculated a rate of 5% without significant differences in length of stay, rate of complications or mortality compared to primary

surgery. Reoperation was however associated with a higher rate of conversion to open surgery with a tendency towards higher rates of conversion in low-volume centers. As in the American study, reoperation was often performed at different centers than the primary procedure. Whether this was the result of centralization or patient's wishes is unknown.

It is our hypothesis, that from 2000-2017, reoperative anti-reflux surgery was performed primarily with a laparoscopic approach without increased length of stay or rate of complications compared to primary surgery. Due to increased surgical experience the rate of complications is decreasing despite increased comorbidity. Endoscopic balloon-dilatation delays reoperation but does not prevent it.

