## Methods

The study is a two-part register-based cohort study based on data from The National Patient Registry, The Civic Registry and Danish Anaesthesia Database in the period 1996-2017. The two individual parts of the study concerns the same population.

The population is defined as all adult Danish patients undergoing anti-reflux surgery (Nomesco: KJBC00, KJBC01, KJBC02, KJBW96, KJBW97) from 2000-2017 identified from The National Patient Register.

Age, sex, Charlson Comorbidity Index at date of surgery and length of stay in relation to any surgery and any surgical or endoscopic procedure performed after anti-reflux surgery (including diagnosis 30 days postoperatively to establish possible morbidity) are derived from the National Patient Registry.

ASA-score, weight, height, use of alcohol or tobacco and priority of any surgery (emergency or planned) during the study period are retrieved from The Danish Anaesthesia Database. From the Civic Register, data on mortality in the study period are retrieved.

Information on the use of pharmacological treatment for gastroesophageal reflux disease on population level is retrieved from MEDSTAT and data on population size on population level are retrieved from Statistics Denmark.

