## Statistical analysis

### 1) Course of illness leading to reoperative anti-reflux surgery

Data will be analyzed using STATA15. Descriptive analysis of age, sex, comorbidity (Charlson Comorbidity Index, ASA-score, BMI, alcohol/tobacco use), complications to surgery, rate of endoscopic dilation and mortality comparing patients with only primary anti-reflux surgery and patients with reoperation during the study period, will be performed using Student's t-test, Chi2-test and Mann-Whitney-U test.

Logistic regression will be performed with reoperation (laparoscopic, open or other) as primary outcome and age, sex, comorbidity (Charlson Comorbidity Index, ASA-score, BMI, alcohol/tobacco use), complications to surgery and endoscopic or surgical procedure during study period as independent variables. If the number of patients is sufficient, subanalysis will be performed with emergency reoperation as dependent variable/outcome.

Secondary analysis will be performed using Cox-regression investigating time to reoperation with age, sex, comorbidity (Charlson Comorbidity Index, ASA-score, BMI, alcohol/tobacco use), complications to surgery and endoscopic or surgical procedure during study period as independent variables.

*2) Utilization of treatment of gastroesophageal reflux disease.*

The rate of anti-reflux surgery per 100.000 inhabitants for each year during the study period will be calculated using census data from Statistics Denmark. From MEDSAT the rate of use of pharmacological anti-reflux treatment per 100.000 inhabitants will be calculated using abovementioned census-data. Trends in the utilization of surgery are investigated with trend-analysis in the form of Poisson-regression alternatively negative binominal regression.

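### The planned models cannot test whether balloon dilation delays reoperation without preventing it, because neither can separate delay from prevention or from no effect

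*Combined protocol and SAP*

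**What the plan says.** The last sentence of the hypothesis paragraph (Background) is "Endoscopic balloon-dilatation delays reoperation but does not prevent it". It makes two claims: reoperation comes later after dilation, and it happens as often in the end.

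Under Statistical analysis, part 1, two regression models could bear on this:

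- The primary model: "Logistic regression will be performed with reoperation (laparoscopic, open or other) as primary outcome". No time horizon is given.
- The secondary model: "Secondary analysis will be performed using Cox-regression investigating time to reoperation".

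Both list "endoscopic or surgical procedure during study period as independent variables". Dilation is named separately only in the descriptive comparison of patients with and without reoperation. In the models it sits inside a pooled procedure covariate that is not described as time-dependent. The plan mentions no time-varying effect, check of proportional hazards, landmark, or cumulative incidence at fixed times. It does not say which analysis tests the dilation hypothesis.

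The cohort is defined by surgery "from 2000-2017 identified from The National Patient Register", so follow-up runs from almost nothing to about 18 years.

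**The concern.** A Cox model with one coefficient assumes that dilation multiplies the hazard by the same factor at all times. Where most patients are never reoperated, a constant ratio below 1 means fewer reoperations throughout, which is prevention. A ratio of 1 means no effect. Delay without prevention is neither of these, since the ratio has to start below 1 and finish above it. Fitting one number to that pattern gives an average whose weights depend on how long patients happen to be followed.

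At stake is whether the study can answer a question it sets itself. If the plan is followed exactly, a ratio near 1 could mean delay only or no effect, and a ratio below 1 could mean delay or prevention. Neither half of the hypothesis could be supported or refuted from the planned output.

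**Working it through.** The plan gives no event count, target ratio or power figure, so there is nothing to reproduce. The check uses the incidences cited in the Background and labelled assumptions.

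**Inputs from the document.** "An American study reported a cumulative five- and ten year incidence of reoperation of 5.2% and 6.9% respectively"; also "The rate of reoperation was highest in the first year after primary anti-reflux surgery".

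**Assumptions (none is in the document).** Size of the delay; share of patients dilated (5% to 30%; this matters little); delay counted from time zero, a simplification.

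**1. Baseline.** Cumulative hazard H0(t) = H0(5) × (t/5)^k.
- H0(5) = −ln(1 − 0.052) = 0.0534
- H0(10) = −ln(1 − 0.069) = 0.0715
- k = ln(0.0715/0.0534)/ln 2 = 0.42, a falling hazard, in line with the excess in the first year.

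**2. What a constant ratio θ implies.** Incidence = 1 − exp(−θ × H0(t)).
- θ = 0.7: 3.7% at 5 years and 4.9% at 10 years, against 5.2% and 6.9%.
- θ = 0.8: 4.2% and 5.6%.

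The gap does not close, so this is prevention within follow-up. For θ = 0.7 the 10-year odds ratio is (0.0488/0.9512)/(0.069/0.931) = 0.69. With events this rare, the logistic model repeats the Cox result.

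**3. What delay without prevention implies.** Take H1(t) = H0(10) × (t/10)^k1 with k1 > k, so both groups reach 6.9% at 10 years. The true ratio at time t is (k1/k) × (t/10)^(k1−k). The single Cox ratio is the large-sample solution of the partial-likelihood equation.

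| k1 | 5-year incidence, dilated | True ratio, year 1 | True ratio, year 10 | Crosses 1 at (years) | Single Cox ratio, 5-year data | Single Cox ratio, 10-year data |
|---|---|---|---|---|---|---|
| 0.6 | 4.6% | 0.94 | 1.43 | 1.4 | 0.88 | 0.99 |
| 0.8 | 4.0% | 0.79 | 1.90 | 1.8 | 0.76 | 0.99 |
| 1.0 | 3.5% | 0.63 | 2.38 | 2.2 | 0.66 | 0.99 |
| 1.5 | 2.5% | 0.30 | 3.56 | 3.1 | 0.47 | 0.98 |

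The hypothesis is exactly true at 10 years in every row, yet the 10-year ratio looks like no effect and the 5-year ratio looks like prevention.

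**4. Pure 2-year shift, groups otherwise at equal risk.** H1(t) = H0(t − 2).

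| Baseline | 5 years | 10 years | 18 years | Spread evenly over 0-18 |
|---|---|---|---|---|
| Cited incidence | 0.80 | 0.90 | 0.94 | 0.83 |
| Hazard ×5 in both groups | 0.75 | 0.85 | 0.90 | 0.79 |

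The size depends on the baseline shape. With a hazard constant within each 5-year period in place of the Weibull, the same shift gives 0.60 at 5 years and 0.89 at 10.

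In the ×5 row, 18-year incidence is 35.3% with the shift against 36.7% without. A constant ratio of 0.79 would give 1 − (1 − 0.367)^0.79 = 30.4%. The Cox output with spread follow-up would be 0.79 in both cases.

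The odds ratio has the same fault, because an event delayed past the end of data counts as none. At the cited incidence, 4.22% against 5.20% at 5 years gives (0.0422/0.9578)/(0.052/0.948) = 0.80. At 18 years, 8.35% against 8.75% gives (0.0835/0.9165)/(0.0875/0.9125) = 0.95.

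**5. The contrast actually planned.** The models cover the whole cohort. If dilated patients are assumed to have five times the hazard of all others, plus a 2-year delay, the Cox ratio is about 3.8 at 5 years, 4.3 at 10 and 4.5-4.6 at 18. It is about 4.0 with spread follow-up, and 5.0 with no delay at all.

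**The case against.** Four arguments deserve an answer.

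*The two models divide the work: logistic regression addresses prevention and Cox addresses delay.* The plan does not say so. The pairing also fails, because the logistic model has no horizon, follow-up is unequal, and dilation is pooled with other procedures. Step 4 shows that the odds ratio mixes delay with prevention as well.

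*Delay without prevention does not always mean non-proportional hazards.* This stands as a qualification. If every patient were eventually reoperated, a constant ratio below 1 would be delay alone. Incidences of 5% to 7% and finite follow-up are far from that case.

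*The figures rest on assumed delays and an assumed fivefold hazard.* This stands too. The figures show a range; the need for a ratio that crosses 1 follows from the algebra.

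*Confounding by indication is the larger problem.* Probably so. The Background says possible dilation should come before reoperation, so dilated patients are likely already on the way to it. None of the listed covariates measures dysphagia or recurrent reflux. The fix below does not remove this.

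The last argument also rules out a stronger reading. A reader might infer that the Cox model will return a ratio below 1 and be reported as showing that dilation reduces reoperation. The documents do not support that. Equal 10-year incidence gives about 0.98-0.99, and a higher-risk dilated group can push the ratio well above 1.

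**Conclusion.** The concern holds in this form: as specified, neither the Cox nor the logistic model can separate delay from prevention or from no effect, so the dilation hypothesis is stated without an analysis that can answer it. In equal-risk groups under a 2-year shift and the Weibull baseline, the single ratio moves from about 0.75-0.80 at 5 years to 0.90-0.94 at 18. With equal 10-year incidence it is about 0.98-0.99 over 10 years. In the whole cohort its direction cannot be predicted (about 3.8 to 4.6 under an assumed fivefold hazard).

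The conclusion rests on the low cited incidence, finite follow-up, and reading the hypothesis as fewer reoperations early and equal numbers later. It does not rest on the falling baseline hazard, which is compatible with proportional hazards. It concerns one of several hypotheses, and the Cox model is a secondary analysis.

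**What to change.** In Statistical analysis, part 1:

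1. Enter balloon dilation as its own time-dependent covariate, separate from other endoscopic and surgical procedures. Give it separate early and late effects by time since dilation, or a dilation-by-log-time term.
2. Base the conclusion on delay and prevention on cumulative incidence of reoperation, with death as a competing event, at a pre-specified early and late horizon from a common landmark (for example 1, 5 and 10 years). Do not base it on one overall hazard ratio or on the logistic odds ratio.
3. State how close late incidence must be to count as not prevented, since a non-significant difference does not show this.
4. State that confounding by indication remains and limits a causal reading.

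The cost is wording and code. The Methods already retrieve later procedures and mortality, and the planned time-to-reoperation analysis already needs event dates. The downside is wider intervals for period-specific estimates.

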**Funding and ethical considerations**

The study is part of a ph.d. thesis and is funded by The Region of Southern Denmark, The University of Southern Denmark, The Department of Surgery, Kolding Hospital and The Research Council at Little Belt Hospital.

The study requires no informed consent in Danish law as the study is register-based. However, permission from The Danish Data Protection Agency and The Danish Health Data Agency will be obtained before the study is commenced.

None of the involved parties have financial interests or conflicts of interest pertaining to this study.

